At the end of the each 6 month period, interviews with study staff and CHWs will be completed for the purpose of program evaluation, and focus groups will be completed with a random sample of existing enrolled CHW intervention participants will assess current satisfaction and usage of CHWs. Questions will also assess barriers and facilitators to the implementation and adoption process of the integrated intervention appropriates, fidelity to the interventions and the solicit recommendations for the replication and scalability of the intervention to other sites. Satisfaction and outcomes from the partnership and capacity building process will also be assessed. Questions will be adapted from existing validated measures on acceptability, feasibility, adoption, organizational culture, and scalability and other previous work.

The key informant interviews as part of the Phase 3 implementation evaluation will include NYULH employees. NYU CHWs served as mentors to the external implementation site, and thus their inclusion in the research is unavoidable, as inclusion of these NYU staff members in the research is important for achieving Specific Aim #3. The unique knowledge obtained from the NYULH employees regarding the training and mentorship they provided to the external site will allow us to delineate factors influencing reach, appropriateness, fidelity, adoption, and maintenance of the intervention within clinical and community settings to optimize intervention replication.

C3. Characterizing the Prevalence of Type 2 Diabetes and Prediabetes

To better characterize differences, similarities, and reach for implementation of the intervention, retrospective analyses will be conducted by extracting variables from the EHR using samples of South Asians aged 18+ years living in the greater Atlanta area and the New York City area from two large healthcare systems. These variables include: 1) study population characteristics (i.e age, gender); 2) prevalence of diabetes and prediabetes; 3) diabetes risk factors (i.e. smoking, BMI), comorbidities (i.e. blood pressure, lipids), 4) diabetes complications (i.e.. neuropathy, nephropathy, and retinopathy); and 5) diabetes/CVD medications among South Asians.

IV. METHODS and PROCEDURES

A. Methods and Procedures

A1. Integrated CHW Intervention

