This study includes the recruitment of a subset of community health workers participating in the project who are NYULH employees, which are considered a vulnerable population given the additional risks of coercion and undue influence that are inherent in research studies conducted in the workplace. Including these employees who are involved in the project in the research is not a matter of convenience; rather, it is essential for program evaluation purposes in order to understand their attitudes toward the mentorship and technical assistance provided to the Emory site in Atlanta. NYU CHWs served as mentors to the external implementation site, and thus their inclusion in the research is unavoidable, as inclusion of these NYU staff members in the research is important for achieving Specific Aim #3. The unique knowledge obtained from the NYULH employees regarding the training and mentorship they provided to the external site will allow us to delineate factors influencing reach, appropriateness, fidelity, adoption, and maintenance of the intervention within clinical and community settings to optimize intervention replication.

NYULH employees recruited as research subjects are more vulnerable to undue influence or coercion because of the possibility that they may perceive employment or other benefits as dependent upon their participation in research. In addition, NYULH employees may experience increased risk of invasion of privacy or loss of confidentiality. To minimize these risks, a study team member with no direct supervisory or evaluation responsibilities will be involved in enrolling the CHWs who are NYULH employees who wish to participate in the key informant interview as well as conducting the interview. At

time of enrollment, the study team member will emphasize that participation is voluntary and refusal to participate will not affect employment or job performance evaluation. Supervisors of these staff will not be involved in any capacity and will not have access to review any identified transcripts or recordings. All identifying information for employees will be kept strictly confidential following the data security provisions outlined in this protocol.

Provider Surveys

Inclusion criteria for the surveys are as follows: adult (18 years and over); clinicians employed by one of the participating clinic sites and have enrolled into the study.

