Exclusion criteria include the following: clinicians who are unable to complete the survey in the English language.

Key Informant Interviews

Inclusion criteria for the interviews are as follows: Adult (18 years and over); must be a provider, clinic manager, or community health worker.

Exclusion criteria include the following: participants who are unable to participate in the interview conducted in the English language.

Focus Groups

Inclusion criteria: Participant previously enrolled in and participated in the CHW intervention (meeting all criteria listed for CHW intervention participant above).

Exclusion criteria: Unwilling to consent to participate

Characterizing Prevalence

Inclusion criteria: a) of South Asian ethnicity (identified by a combination of using natural language processing to identify common South Asian surnames in the EHR, race/ethnicity, and language preference); b) 18 years of age or older; and c) had appointment with a physician for routine non-emergent primary care in the last twelve months.

Exclusion criteria: a) pregnant at time of visit; or b) type 1 diabetes or diabetes secondary to other conditions (e.g. steroid-induced, pancreatic insufficiency, or chemotherapy-induced).

VI. STUDY SCHEDULE

A. Method of Subject Identification and Recruitment

CHW Screening Period

There will be a 1-month recruitment period. All participants will be sent an invitation letter (See Recruitment Letter for CHW Intervention) to participate in the CHW intervention. Invitation letters will be followed up with phone calls by CHWs (See Script for Telephone Screening for CHW Intervention), during which CHWs will explain the study and elements of informed consent. Participant names, telephone numbers, and email addresses will be needed in order for CHWs to contact participants regarding participation in the intervention (See Application for Waiver of HIPAA). In addition, a screening form (See Telephone Screening Form for CHW Intervention) will be completed to verify eligibility. CHWs will call patients a maximum of 10 times over a two-week period at varying times of day to invite them to enroll into the study. Once the participants agree to enroll in the study, they will come into the Emory Dunwoody

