Clinic to sign the consent form and complete the baseline survey. Control participants will not be contacted during the intervention and will only be contacted once the intervention with treatment participants has been completed; those who were control in the first wave of recruitment can then be enrolled in the second wave. Due to the study funding period, those in the second wave control arm will be offered education sessions as a point of service and not as part of research.

CHW Intervention Period

There is a 6-month intervention period immediately following recruitment. Each session will be held multiple times throughout the month to accommodate a variety of schedules by the treatment participants. Month 1 has participants coming to Session 1 followed by one follow-up phone call. Month 2 has participants coming to Session 2 followed by one follow-up phone call and then one in person visit at the participant's home or at local meeting point used for a session. Month 3 has participants coming to Session 3 followed by two follow-up phone calls within the month. Month 4 has participants coming to Session 4 followed by one follow-up phone call and then one in person visit at the participant's home or at local meeting point used for a session. Month 5 has participants coming to Session 5 followed by two follow-up phone calls within the month. Month 6 concludes the intervention period with an endpoint survey and completion certificate.

Provider Surveys

Over the course of 2 months, providers at participating practices will be invited to complete the Provider Survey via email link. Paper surveys will also be available for those who prefer to fill out the survey in hard copy. No undue pressure will be given to subjects for participation as the participation is entirely voluntary and will be described via email or verbally to the invited participants (See Invitation Script and Elements of Informed Consent for Provider Survey).

Key Informant Interviews

Over the course of 2 months, participating providers and community health workers will receive an invitation to participate in the interview (See Invitation Script and Elements of Informed Consent for Key Informant Interview). No undue pressure will be given to subjects for participation as the participation is entirely voluntary (See Verbal Consent Script for Key Informant Interview).

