B3. Sampling. Across the three clinical sites, there will be approximately 3,600 unique South Asian patients that have had an office visit in the last year. Based on preliminary analysis of [name] patient panel, we estimate 30% of those individuals will have a Type II Diabetes diagnosis (n=1080), and estimate that 60% will have co-morbid diabetes and HTN (n=648), 75% of these individuals will have uncontrolled HTN (n=486), and additional 5% will be excluded due to not meeting other eligibility criteria, leaving 462 individuals eligible for the study. Of these individuals, approximately 50% will be randomized to the treatment group, and we estimate based on our previous studies that 40% of patients will be interested in the study and consent to enroll into the study (n=326). Based on retention rates from our CHW studies,^{12,95,96,98,128,129,131} we estimate that approximately 90% of individuals in control and treatment quarters will be followed up at six months (n=83). Thus, across sites, we will enroll approximately 652 patients per six-month period, resulting in total recruitment of approximately 326 treatment group participants across 3 practice sites. Treatment group participants will be matched to 326 control group participants. Approximate CHW caseload over a six-month period is 16 participants for a full-time CHW.

Specific Aim 3 Analysis.

B4. Analysis to address this aim will be guided by the questions in **Table 4**.

Table 4: Guiding Questions

Utilization Patterns	
 • How frequently do clinicians utilize the intervention? • What is the percentage of adoption? • Does the utilization pattern change over time?
Physician Attitudes Regarding the Integrated Intervention	
 • What are physicians' attitudes regarding CHW approaches to diabetes and HTN management? • How satisfied are the physician's with the integrated intervention tools? • What are the barriers and facilitators of using the CHW integration components? • How does the intervention affect clinicians' satisfaction with workflow around T2DM management?

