Barriers and Facilitators to Implementation Adoption and Implications for Scalability	
 • What organizational barriers and facilitators appear to influence implementation and how? • Did members of the practice understand and respect the respective roles of each team member? • How did this organization customize the intervention to better serve its own local needs? • How were users involved in design and implementation? • Did CAB member feel ownership in the partnership process? • What are recommendations for replicating this model for other clinical settings and communities?

1. Utilization Patterns. Data from REDCap tracking forms will be used to analyze utilization patterns of the intervention (e.g. referral to CHW, receipt of CHW feedback on patients' progress and referrals). These data will yield descriptive trends for frequency of utilization across the participating clinic sites.

2. Physicians 'Attitudes Regarding the Integrated Intervention. Physician attitudes will be primarily assessed with data from brief surveys collected from the participating clinicians. Survey items with response scales will be designed to capture data on each of the research questions above. For instance,

participants may be asked to respond on a five-point scale (from 1=strongly agree to 5=strongly disagree) to the following statement: "CHWs are helpful to me". The survey data come from a small sample (n=approximately 10) and are only intended to quantify descriptive information and not for extensive statistical analyses. The data will be tabulated and summarized descriptively to assess change in attitudes from baseline to 12 months.

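### Table 4 asks whether CAB members felt ownership of the partnership, but no survey, interview or focus group category admits CAB members as such

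*Combined protocol and SAP*

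**What the plan says.** Specific Aim 3 (section II.B) sets out to identify what influences reach, adoption, fidelity and maintenance, so that the intervention can be replicated. Section VII.B4 says the analysis is guided by Table 4. Two of its questions are "What is the percentage of adoption" (under utilization patterns) and "Did CAB member feel ownership in the partnership process" (under barriers, facilitators and scalability).

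The people who can supply data are set out in several places:

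- **Provider survey, eligibility (section V.A):** "clinicians employed by one of the participating clinic sites and have enrolled into the study".
- **Provider survey, design (section III.C1):** goes to the participating physicians, n=10.
- **Provider survey, invitation (section VI.A):** "providers at participating practices will be invited to complete the Provider Survey via email link".
- **Interviews, eligibility (section V.A):** the informant "must be a provider, clinic manager, or community health worker".
- **Interviews, invitation (section VI.A):** "participating providers and community health workers will receive an invitation to participate in the interview".
- **Interviews, design (section III.C2):** "interviews with study staff and CHWs will be completed for the purpose of program evaluation".
- **Focus groups (section V.A):** people who were enrolled in, and took part in, the CHW intervention.

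Section III.C2 also says that satisfaction with the partnership and capacity-building process will be assessed, without naming who will be asked. The only other task given to the CAB in the analysis plan is to review the initial qualitative codes (section VII.B4, item 3).

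**The concern.** A question about what CAB members felt has to be put to CAB members. If the eligibility rules are followed as written, none is approached in that role, and ownership can be reported only second-hand by clinic staff and CHWs, or by a CAB member who happens to qualify for another reason. These are stated inclusion criteria rather than silence, so the team could not interview CAB members as such without an amendment.

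The clinician side has a related but weaker problem. The survey criterion requires enrolment, and interview invitations go to participating providers. Clinicians who did not take up the intervention may therefore not be asked why. Table 4 also seeks recommendations for other clinical settings, and there the reasons for non-uptake matter most. The survey is "only intended to quantify descriptive information and not for extensive statistical analyses", so no later modelling could make up for people who were never asked.

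**Working it through.** No power or error-rate input bears on this. The check is a head count followed by a comparison of the rules.

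**Step 1. Head count.** Inputs from section V.A are 652 trial participants, 10 provider surveys, 25 key informant interviews and 50 focus group participants.

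652 + 10 + 25 + 50 = 737.

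This equals the stated total, so every expected subject is assigned to a named group and none is a CAB group. The retrospective EHR review has no respondents.

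**Step 2. Routes open to a CAB member.**

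- *Provider survey:* only as a clinician at a participating site.
- *Interview:* only as a provider, clinic manager or CHW.
- *Focus group:* only as a past intervention participant.
- *Code review:* the CAB comments on codes and does not supply data.

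No route is open by virtue of CAB membership.

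**Step 3. Share of Table 4 affected.** The three rows hold 3 + 4 + 6 = 13 questions. One of the 13 concerns CAB ownership.

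**Step 4. Clinician rules side by side.**

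- *Survey:* eligibility requires enrolment and the design section says participating physicians, while the invitation covers providers at participating practices with no enrolment condition. A non-enrolled clinician at a site would be invited and then found ineligible.
- *Interview:* eligibility carries no enrolment condition and admits clinic managers, while the invitation names only participating providers and CHWs, and the design section names only study staff and CHWs. A non-participating clinician or a clinic manager would be eligible but not invited.

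Under each route, at least one rule leaves out the clinician who did not take part.

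**Step 5. Whether another source fills the gap.** REDCap tracking forms (section VII.B4, item 1) supply utilization, such as referrals to the CHW and feedback received. They show how often clinicians used the intervention, not why some did not. They can inform the percentage of adoption, although its denominator is not stated. Focus groups are part of the evaluation of barriers, but their members are patients who received the intervention.

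**The case against.** The strongest reply is that adoption is well covered. Providers, clinic managers and CHWs are among the people whom adoption concerns, and interview eligibility admits all three without an enrolment condition. The percentage of adoption is a utilization measure drawn from tracking data, so it does not depend on survey eligibility. The plan never says that an enrolled clinician is one who adopted. Practices sign a memorandum, physicians are encouraged to refer, and clicking the survey link counts as consent. Being enrolled may therefore mean no more than agreeing to be surveyed, and a clinician could be enrolled yet never refer a patient.

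Much of this stands. A reader might infer that the adoption questions cannot be answered at all, or that every clinician asked will already be an adopter; the documents support neither. What survives is the mismatch between eligibility and invitation, which under a restrictive reading of enrolment leaves non-adopters out.

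On the CAB, it can fairly be said that the documents do not define it. If it resembles the Atlanta South Asian Health Alliance (ASHA) advisory board described in section III.A, it includes physicians and patients with diabetes, some of whom might qualify as a provider or a past participant. So a reader should not conclude that CAB members are wholly barred. But qualifying in another capacity is not the same as being asked as a CAB member, and the general promise to assess the partnership names no CAB respondent. The interview guides are listed in the appendix by title only, so their contents prove nothing either way.

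**Conclusion.** The CAB point holds. One of 13 guiding questions has no designated respondents, and the full count of 737 leaves no place for them. This needs no assumption about who sits on the CAB, because it rests only on the respondent categories as written.

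The clinician point holds as a secondary one. The survey and interview rules disagree among themselves, and reasons for not adopting are likely to be under-represented. How far depends on what enrolment and participation mean for a clinician, which the plan does not say. It is tempting to put a number on the resulting bias, but the documents give neither the number of clinicians at the sites nor any expected difference in attitude, so no figure is supportable.

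Aim 3 is descriptive and qualitative, and the primary BP comparison is untouched. This is a modest amendment, worth making before the interviews begin.

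**What to change.** 1. In section V.A, add community advisory board member as a further eligible category for key informant interviews, and add the same group to the interview invitation in section VI.A. Keep within the planned 25 interviews. The cost is a few fewer interviews with providers and CHWs, and a check that the interview guide asks about ownership. The English-language requirement for interviews would still apply.
2. In the provider survey criteria in section V.A, delete the enrolment condition so that eligibility matches the invitation in section VI.A, and bring section III.C1 into line. The cost is a few more emailed links and possibly more than 10 respondents, in which case the 737 total must be updated.
3. In section VI.A, extend the interview invitation to non-participating clinicians and to clinic managers at the sites, and align section III.C2. This too draws on the 25 slots.

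I would not split the survey results by whether a clinician referred a patient. CHWs also recruit directly from EHR lists and at community events, so referral is a weak marker of adoption, and subdividing about 10 respondents could make individuals recognisable.
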